TITLE: Identification of exercise components of core stability and their effectiveness on foot posture, foot function and lower limb alignment in adults with flexible flat feet

NCT number: NCT06567509

IREC ETHICAL APPROVAL NUMBER: IREC 2024-257

DATE OF DOCUMENT: 16/07/2024

DOCUMENT TYPE: Study Protocol

BACKGROUND

Flexible flat feet are a common clinical condition that may influence lower limb alignment and proximal joint biomechanics. Conventional foot-focused exercises are commonly prescribed; however, their effects may be limited. Emerging perspectives suggest that altered foot posture may be influenced by proximal postural and neuromuscular factors, including core musculature function. Therefore, this study aimed to examine the effect of core stability exercises on foot posture and lower limb alignment in individuals with flexible flat feet

Objectives

1. To evaluate the feasibility of core stability training protocol that will be devised in the proposed study.
2. To assess the effect of core stability training on the foot posture in adults with flexible flat feet.
3. To assess the effect of core stability training on lower limb alignment in adults with flexible flat foot.

STUDY DESIGN

- Randomized Controlled Trial
- Allocation: parallel
- Number of groups: 2
- Study duration: December 2024 to January 2026
- Study was conducted at Department of Physical rehabilitation Sciences, International Islamic university of Malaysia, Kuantan, Pahang, Malaysia.

PARTICIPANTS

- **Participants were recruited from general student population around Kuantan with following criteria:**
 - Inclusion Criteria
 - ✓ Subjects of age group 18 to 30 years.
 - ✓ Both males and females.
 - ✓ No recent history of lower limb injuries.
 - ✓ Subjects with bilateral flexible flat feet as per the definition.
 - ✓ Subjects with positive navicular drop test ($> 10\text{mm}$) and positive Jack's test.
 - Exclusion criteria
 - ✓ Rigid flat foot
 - ✓ Subject who are involved in a specific sport at least 2 h /day and 3 times a week regularly.
 - ✓ History of arthritic symptoms of lower limb joints.
 - ✓ History of any ligament or tendon injuries around ankle, knee, or hip joint.
 - ✓ History of any limb surgery or back surgery.
 - ✓ Chronic back pain.
 - ✓ Any history of neurological deficit or diabetic neuropathy.

INTERVENTIONS

Experimental Group

Six-week exercise protocol with progression developed following systematically reviewing bod of evidences and tested for feasibility and acceptability in pilot trial.

Exercises	Repetitions and phase wise progression	Rest period between exercise sets
Warm up (Back arching and knee rolling)	3 times each exercise	5 sec rest between exercises
Abdominal hollowing	Repeat until the subject learns to contract core muscles.	5 sec rest between each trial
Curl ups with hands behind head	Phase 1: 10 rept \times 3 times Phase 2: 15 rept \times 3 times Phase 3: 20 rept \times 3 times	120 sec rest between the sets
Bridges with leg lifts	Phase 1: 15 sec hold \times 3 times Phase 2: 20 sec hold \times 3 times Phase 3: 25 sec hold \times 3 times	120 sec rest between the sets
Side bridges	Phase 1: 15 sec hold \times 3 times Phase 2: 20 sec hold \times 3 times Phase 3: 25 sec hold \times 3 times	120 sec rest between the sets
Planks on feet	Phase 1: 15 sec hold \times 3 times Phase 2: 20 sec hold \times 3 times Phase 3: 25 sec hold \times 3 times	120 sec rest between the sets
Quadripedal stance with contralateral arm and leg raise.	Phase 1: 15 sec hold \times 3 times Phase 2: 20 sec hold \times 3 times Phase 3: 25 sec hold \times 3 times	120 sec rest between the sets
Cool Down	Self-stretching of hamstrings and calf in long sitting position 3 times with 10 sec hold.	

Control Group

Conventional foot exercises for control group (3 times weekly for 6 weeks) adapted from previous studies.

A. Warm up:

Active ROM exercise (Knee and hip flexion) 10 repetitions \times 2 sets)

B. Training:

- Active dorsiflexion exercises in long sitting (10 sec hold \times 15 repetitions \times 2 sets)
- Active plantarflexion exercises in long sitting (10 sec hold \times 15 repetitions \times 2 sets)
- Active inversion exercises in long sitting (10 sec hold \times 15 repetitions \times 2 sets)
- Active eversion exercises in long sitting (10 sec hold \times 15 repetitions \times 2 sets)

C. Cool down:

- Calf stretches in long sitting for 10 seconds hold \times 3 sets.

OUTCOME MEASUREMENTS

• Rearfoot Angle (Right & Left)

Rear foot angle was measured by testers using Goniometer in standing position.

• Staheli Plantar Arch Index (SPAI) (Right & Left)

SPAI was measure using footprint method and calculation of arch index

• Q Angle (Right & Left)

Q angle was measure using Goniometer.

ASSESSMENT TIMELINE

- Baseline
- Post Intervention after 6 weeks

SAMPLE SIZE

- Initially Pilot trial started with a sample size of 20 for assessing feasibility
- After completion of protocol, a sample size of 62, determined using G power was recommended.

SAMPLING

- Participants were recruited using convenience sampling and randomly assigned to either the experimental (core stability) group or control (conventional exercises) group. Randomization was performed using a blinded lottery method, in which eligible participants were coded, and the codes were placed in a container. An independent assessor randomly allocated participants to each group using these codes.

BLINDING

- Assessors were blinded to group allocation during the randomization process. Participants and intervention-givers were not blinded due to the nature of the exercise intervention.

STATISTICAL ANALYSIS

- Changes scores (Post mean – Pre mean) were calculated and multivariate analysis was conducted with BMI as a covariate.

ETHICAL CONSIDERATIONS

- Ethics approval was obtained from IREC, Research management centre, International Islamic University of Malaysia with protocol Id -IREC 2024-257
- Written informed consent was obtained from all participants prior to enrolment.

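### The stated change-score analysis adjusts for BMI but not for the baseline value of each outcome, so it gives up precision and leaves the estimate exposed to chance baseline imbalance

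*Combined protocol and SAP*

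**What the plan says.** The STATISTICAL ANALYSIS section reads, in full: "Changes scores (Post mean – Pre mean) were calculated and multivariate analysis was conducted with BMI as a covariate". No other model, secondary analysis or sensitivity analysis appears anywhere, and no section says that a baseline outcome value enters the model.

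The OUTCOME MEASUREMENTS section lists three continuous outcomes, each on two sides: "Rearfoot Angle (Right & Left", "Staheli Plantar Arch Index (SPAI) (Right & Left" and "Q Angle (Right & Left". That makes six measures. The ASSESSMENT TIMELINE has a baseline assessment and one later assessment, "Post Intervention after 6 weeks", so the baseline value of every measure is collected.

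The design section gives "Number of groups: 2". Under SAMPLE SIZE, "a sample size of 62, determined using G power was recommended". On allocation, the SAMPLING section says "Randomization was performed using a blinded lottery method, in which eligible participants were coded, and the codes were placed in a container". It gives no allocation ratio and describes no stratification or balancing on baseline foot posture.

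**The concern.** In the stated model the baseline value enters only by subtraction. That fixes the slope of the 6-week value on the baseline value at 1. If the true slope is below 1, as it is with equal SDs whenever r is below 1, subtraction over-corrects. An arm that by chance starts with higher values will, on average, show a more negative change for that reason alone. BMI protects against this only as far as it is correlated with the baseline outcome.

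Two things are at stake. The confidence interval is wider than the collected data allow. And in a trial of this size the result for any one outcome partly reflects the baseline difference that happened to occur. Nothing in the described allocation limits that difference.

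**Working it through.** **Inputs.** From the document: total 62, two arms, one baseline and one 6-week value, BMI as the only covariate. Assumed, because not stated: 31 per arm (1:1), equal SDs at the two times, and r from 0.5 to 0.9. The document gives no correlation or reliability figure.

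**1. The plan's own figure.** The 62 can be neither confirmed nor refuted, because alpha, power, effect size and dropout are not given. Several assumed sets reach it with a two-sided 5% t-test: a standardised effect of 0.73 at 80% power, 0.85 at 90% power, or 0.80 at 80% power with 15% dropout. The point uses 62 only as the number analysed.

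**2. Precision, before BMI is considered.** In units of SD²:
- change score: 2(1 − r)
- baseline-adjusted: 1 − r²
- ratio, adjusted to change: (1 + r)/2

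| r | Change | Adjusted | Ratio | 62 × ratio |
|---|---|---|---|---|
| 0.5 | 1.00 | 0.75 | 75% | 46.5, about 47 |
| 0.7 | 0.60 | 0.51 | 85% | 52.7, about 53 |
| 0.8 | 0.40 | 0.36 | 90% | 55.8, about 56 |
| 0.9 | 0.20 | 0.19 | 95% | 58.9, about 59 |

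As an illustration only, power for a 0.5 SD effect at 31 per arm (two-sided 5%, normal approximation) goes from 50% to 62% at r = 0.5, 72% to 79% at 0.7, 88% to 91% at 0.8, and 99.3% to 99.5% at 0.9.

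**3. With BMI in both models.** Assume BMI correlates 0.3 with baseline and acts on the 6-week value only through it. The baseline variance not explained by BMI is 1 − 0.3² = 0.91. The change-score residual variance becomes (1 − r)² × 0.91 + (1 − r²), and the adjusted one stays at 1 − r².
- r = 0.5: 0.75 / (0.2275 + 0.75) = 77%
- r = 0.7: 0.51 / (0.0819 + 0.51) = 86%
- r = 0.8: 0.36 / (0.0364 + 0.36) = 91%
- r = 0.9: 0.19 / (0.0091 + 0.19) = 95%

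These leave out the small cost of estimating one more slope with 62 participants. Simulation under the same assumptions includes it. With 40,000 trials per value of r, the ratios were 78%, 88%, 93% and 97%. A run of 4,000 trials at r = 0.5, 0.7 and 0.9 gave 80%, 86% and 97%, which shows the simulation noise.

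**4. Chance imbalance.** The standard error of the baseline difference is √(2/31) = 0.254 SD. Without BMI, a baseline difference D shifts the change-score contrast by −(1 − r)D. For D of one standard error:
- r = 0.5: 0.5 × 0.254 = 0.13 SD
- r = 0.7: 0.3 × 0.254 = 0.08 SD
- r = 0.9: 0.1 × 0.254 = 0.03 SD

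In the 4,000-trial simulation with BMI in both models, the change-score estimate correlated −0.45, −0.36 and −0.19 with the baseline difference at r = 0.5, 0.7 and 0.9. With the baseline covariate the correlation was about 0.

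**5. Average bias.** With a true effect of 0.5 SD, both estimators averaged 0.50 at every r. The shifts in step 4 cancel over repeated randomisations.

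**6. Change or 6-week value.** Once baseline is a covariate, subtracting it from the response changes only its own coefficient, by 1. The group estimate is the same either way, and the simulated estimates agreed to rounding error.

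**The case against.** The strongest defence is that allocation is random, so the change-score contrast is unbiased, and step 5 bears this out. A reader might infer that the planned analysis is invalid or systematically favours one arm. The document does not support that. The imbalance effect is conditional on the baseline difference that occurs, and a difference of two standard errors arises in only about 5% of trials for any one outcome.

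Second, r is unknown and could be high. At 0.9 the variance gain is 5% before the cost of the extra slope and about 3% after it. Goniometer and footprint error would lower r, but no reliability figure is given, so a large loss cannot be asserted. This limits the size of the point, not its direction.

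Third, BMI is already in the model and recovers some of the loss. At the assumed correlation of 0.3 it recovers little (step 3).

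Fourth, the sentence is short, and a baseline covariate may have been intended. It is not specified, though, and an unreported covariate is not a planned one.

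A reader might also take the wording about post and pre means to say that changes are computed from group means. That reading is strained. A model with BMI as a covariate needs one value per participant, so the phrase is most plausibly loose wording for post minus pre. It is not counted as a defect here.

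**Conclusion.** The point holds as a matter of efficiency and of conditional accuracy, not of validity. The only stated model omits a covariate that is collected for every outcome.

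The direction is secure: with equal SDs, (1 + r)/2 is below 1 for every r below 1, apart from the one degree of freedom spent. The size is not. It runs from a variance reduction of roughly a quarter at r = 0.5 to a few percent at r = 0.9. The change-score contrast shifts by 0.13 SD down to 0.03 SD for each standard error of baseline difference. These figures rest on equal SDs, 1:1 allocation and the assumed range of r. Those with BMI also rest on the assumed correlation of 0.3.

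The improvement uses data already in hand and should be made.

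**What to change.** In the model for each outcome and side, add the baseline value of that same outcome and side as a covariate alongside BMI. Report the adjusted group difference with its 95% CI. Change scores may stay as the response. Stating that the change is calculated for each participant would settle the wording.

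The cost is one sentence and no new data. With separate models it is one degree of freedom each: residual degrees of freedom go from 62 − 3 = 59 (intercept, group, BMI) to 58. If a single joint multivariate model of all six measures is kept, up to six baseline covariates enter, leaving 62 − 9 = 53. The plan should say which of these its multivariate analysis means.

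The analysis section is written in the past tense. If the analysis has already been run, the stated model should remain on record and the baseline-adjusted model should be reported as an added, disclosed analysis.
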